PICCOLO is a large randomised trial designed to address both of these modifications, while at the same time acquiring translational scientific information to further refine and direct these treatments in the future. A common control arm of standard single-agent irinotecan will be compared, on the one hand, with ciclosporin-modulated irinotecan and, on the other, with irinotecan plus panitumumab.

The large majority of patients entering PICCOLO will not have received a prior EGFR-inhibiting drug. However, the trial is open to patients following first-line treatment in COIN, one-third of whom will have received cetuximab. These anti-EGFR targeted therapy pre-treated patients will not be included in the primary +/- panitumumab phase III efficacy comparison, but will provide the opportunity to explore, in a randomised phase II analysis, the possibility that EGFR blockade contributes to the efficacy of second-line chemotherapy independent of its use during first-line treatment.

On this basis, PICCOLO opened to recruitment in December 2006 as a 3-arm Randomised Controlled Trial (RCT), with all patients randomised, in equal proportion, to the three study arms **Ir** (standard single-agent irinotecan), **IrCs** (irinotecan at 40% standard dose in combination with ciclosporin), and **IrPan** (standard irinotecan in combination with panitumumab).

K-RAS Mutations and anti-EGFR mAb therapy (section added for Protocol Version 3.0)

Following initiation of the PICCOLO Trial as a 3-arm randomised trial, new data have emerged to suggest that patients can benefit from the application of a molecular selection strategy. This new data necessitates a modification of the original PICCOLO trial design.

K-RAS, the human homolog of the Kirsten rat sarcoma-2 virus oncogene, encodes a GTP-binding protein that acts as a self-inactivating signal transducer by cycling from GDP- to GTP-bound states in response to stimulation of cell surface receptors including EGFR.^{26,27} Certain codons in *K-RAS* (12, 13 and 61) are common sites of mutations that yield constitutively active protein.^{28,29} Such mutations are found in approximately 30-50% of colorectal cancers.³⁰ The presence of mutant *K-RAS* in lung and colorectal cancers is a poor prognostic factor,^{30,31} and several reports from non-randomised series suggested association with lack of response to EGFR inhibitors.^{32,33}

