5.2 Randomisation

A verbal explanation of the PICCOLO Patient Information Sheet and Consent Form document will be provided by the attending hospital staff for the patient to consider and a paper copy provided to the patient. This will include detailed information about the rationale, design and personal implications of the study. Following information provision, patients will have as long as

they need to consider participation (normally a minimum of 24 hours) and will be given the opportunity to discuss the trial with their family and healthcare professionals before they are asked whether they would be willing to take part in the trial. After the patient has provided written informed consent and has been confirmed as eligible the patient may be randomised.

Patients who fulfil the eligibility criteria, and have given signed informed consent, and whose *K-RAS* status has been determined as **mutation**, or whose *K-RAS* status is **unknown**, will be randomised on a 1:1 basis to receive either standard **Ir** or **IrCs**.

Patients who fulfil the eligibility criteria, have given signed informed consent, and whose *K-RAS* status has been determined as **wild-type** and **have not** previously received an anti-EGFR targeted therapy will be randomised on a 1:1 basis to receive either standard **Ir** or **IrPan**.

Patients who fulfil the eligibility criteria, have given signed informed consent, and whose *K-RAS* status has been determined as **wild-type** and **have** previously received an anti-EGFR targeted therapy will be randomised separately on a 1:1 basis to receive either standard **Ir** or **IrPan**.

Randomisations will be achieved using dynamic allocation incorporating a random element, via a computer-generated programme, to ensure treatment groups are well-balanced for the following patient characteristics, details of which will be required for randomisation:

- Randomising centre
- Previous treatment with oxaliplatin (no –vs– yes)
- Previous treatment with bevacizumab (no –vs– yes)
- Best response to any previous drug therapy (response/stable disease –vs– progressive disease alone –vs– unknown)
- Required dose reduction or delay for toxicity during previous therapy (yes –vs– no)
- WHO performance status (0 or 1 –vs– 2)

The person telephoning to randomise the patient should have the completed Randomisation Checklist in front of them at the time of telephoning as the following additional information will be required at randomisation:

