7.2 Pre-randomisation Assessments

Post written informed consent and prior to randomisation, the following investigations and assessments will be carried out:

- Medical history including prior treatment with 5FU, capecitabine, oxaliplatin, bevacizumab or an anti-EGFR targeted therapy,, best response to previous drug therapy and dose delays/reductions for toxicity during previous drug therapy. Details of concomitant disease and medication will also be collected.
- Physical examination including height, weight, body surface area and WHO performance status
- Laboratory tests including FBC, LFTs, U&Es
- If the patient is female and of childbearing potential, a negative serum or urine HCG pregnancy test within 72 hours of trial entry
- Baseline Quality of Life questionnaires (for details please refer to section 7.8)

In addition the following data will be collected:

- Patient's GP name and address
- Patient's personal details and demographics

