Since previous anti-EGFR targeted therapy use is of no concern for the Ir vs. IrCs comparison, this analysis will include all patients randomised to receive either Ir or IrCs under Protocol Version 1.0, and all patients randomised to receive either Ir or IrCs via the Ir vs. IrCs randomisation in this amended protocol, regardless whether or not they have previously used anti-EGFR targeted therapy.

The two primary comparisons of Ir vs. IrCs and Ir vs. IrPan are essentially two independent comparisons⁴¹. We therefore aim to recruit 480 patients who have wild-type *K-RAS* status and who have not previously received an anti-EGFR targeted therapy (240 patients per arm) to the Ir vs. IrPan comparison. However, dependent upon the proportion of patients with unknown *K-RAS* status, there may be some over-recruitment to this comparison. We expect approximately 15% of all patients recruited to this comparison to have previously received an anti-EGFR targeted therapy therefore the expected sample size for the exploratory analysis of Ir vs. IrPan for those patients previously receiving an anti-EGFR targeted therapy (and who have wild-type *K-RAS* status) is approximately 86 patients (43 patients per arm of Ir/IrPan).

K-RAS status

We expect that the split between mutant *K-RAS* status and wild-type *K-RAS* status will be approximately 42:58, and that approximately 15% of patients will have unknown *K-RAS* status. The proportion of patients with unknown status will be monitored as this figure may vary. Only patients with wild-type *K-RAS* status will be randomised to the Ir vs. IrPan comparison. There will, however, be some patients randomised to IrPan via protocol Version 1.0 who will have either mutant or unknown *K-RAS* status. We anticipate that approximately 167 mutant or unknown *K-RAS* status patients will have been randomised to receive either Ir or IrPan under Protocol Version 1.0, of whom approximately 19 will have previously received an anti-EGFR targeted therapy. An exploratory analysis will be carried out on these patients.

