Analysis will be based on the lower limit of the 95% confidence interval (CI) (one-sided type I error rate of 2.5%) of the difference in proportion of patients progression free at 12 weeks from randomisation between each treatment group. Logistic regression will also be used to adjust for the minimisation factors, previous anti-EGFR targeted therapy use and any other covariates identified to influence patients' prognosis. Treatment and covariate estimates with corresponding 95% CIs will be given. To account for any deaths from causes other than colorectal cancer which may occur within 12 weeks of randomisation, for whom no evidence of disease progression was found, sensitivity analyses will be conducted classifying these patients as progression-free (these patients will be classed as having progressive disease at 12 weeks in the main analysis). Sensitivity analysis will also be conducted to account for patients with missing data regarding progression at 12 weeks, using the local assessment or classifying these patients as with progressive disease, as appropriate. The primary analysis will be based on the lower limit of the confidence interval of the odds ratio for the proportion of patients progression free at 12 weeks, obtained using logistic regression which adjusts for the minimisation factors.

Secondary Endpoints

The difference in proportion of patients who are free from treatment failure, defined as clinical or radiological progression, death due to colorectal cancer or toxicity, or termination of treatment irrevocably, at 12 weeks from randomisation between treatment groups will be compared using a two-sided chi-squared test. Logistic regression will also be used to adjust for the minimisation factors, previous anti-EGFR targeted therapy use and any other covariates identified to influence patients' prognosis. Treatment and covariate estimates with corresponding 95% CIs will be given. Sensitivity analyses will be conducted to allow for any deaths from causes other than colorectal cancer within 12 weeks of randomisation. Sensitivity analysis will also be conducted to account for patients with missing data regarding treatment failure at 12 weeks, classifying these patients as with treatment failure.

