Should non-inferiority of IrCs to Ir be shown, we will consider both treatment groups together, and conduct exploratory subgroup analyses comparing patients' outcome according to the clinical minimisation factors and previous anti-EGFR targeted therapy use.

Ir vs IrPan comparison (patients with wild-type K-RAS status not previously receiving an anti-EGFR targeted therapy)

Patients with wild-type *K-RAS* status randomised via the 'no previous anti-EGFR targeted therapy use' randomisation will be included in this comparison.

Primary Endpoint

Overall survival curves will be calculated using the Kaplan Meier method and compared using a 2-sided log-rank test. OS will also be compared between the control and experimental groups using multivariate modelling. Cox's proportional hazards model, if appropriate, will be used to adjust for the minimisation factors and other important prognostic factors. HRs and corresponding 95% CIs for OS will be presented. Primary analysis will be based on the multivariate analysis which adjusts for the minimisation factors.

Secondary Endpoints

The difference in proportion of patients who are progression-free at 12 weeks from randomisation between treatment groups will be compared using a two-sided chi-squared test. Logistic regression will also be used to adjust for the minimisation factors and any other covariates identified to influence patients' prognosis. Treatment and covariate estimates with corresponding 95% CIs will be given. To account for any deaths from causes other than colorectal cancer which may occur within 12 weeks of randomisation, for patients who have no evidence of disease progression, sensitivity analyses will be conducted classifying these patients as progression-free (these patients will be classed as with progressive disease at 12

weeks in the main analysis). Sensitivity analysis will also be conducted to account for patients with missing data regarding progression at 12 weeks, using local assessment data or classifying these patients as with progressive disease, as appropriate.

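### The primary Ir vs IrPan survival model should carry WHO performance status as 0, 1, 2 instead of 0 or 1 against 2: a small gain at no cost

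*Protocol*

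**What the plan says.** - **Allocation (Section 5.2).** Performance status is one of six minimisation factors and has two levels: "WHO performance status (0 or 1 –vs– 2".
- **Primary survival model (Section 12, Ir vs IrPan, Primary Endpoint).** A log-rank test and a Cox model are both described. The Cox model "will be used to adjust for the minimisation factors and other important prognostic factors". The section then settles which result counts: "Primary analysis will be based on the multivariate analysis which adjusts for the minimisation factors".
- **Data collected.** Section 4 admits status 0, 1 or 2. Section 7.2 lists among the assessments done before randomisation: "Physical examination including height, weight, body surface area and WHO performance status".
- **Sample size (Section 11.1).** 246 deaths in 466 patients give 80% power at two-sided 5% for a 30% reduction in hazard, using a log-rank test with no covariates. The target is 480 patients, to allow for loss to follow-up.

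**The concern.** The protocol names its primary survival model by reference to a list, and that list gives performance status in merged form. Merging 0 with 1 is reasonable for minimisation, where few levels help balance. A model has no such need. If survival differs between status 0 and status 1, the merged factor leaves that difference in the unexplained part of the hazard. A Cox model that omits a prognostic covariate gives a treatment estimate pulled towards no effect, and it does not correct a chance imbalance between arms in that covariate. The result is some loss of efficiency in the analysis that decides the panitumumab question.

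**Working it through.** **1. The plan's own figure.** Inputs from Section 11.1: hazard ratio 0.70, two-sided 5%, 80% power, 1:1 allocation, control median 9 months.

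- Deaths (Schoenfeld) = 4(1.960 + 0.842)² / (ln 0.70)² = 4 × 7.849 / 0.1272 = 247. The plan says 246.
- Power at 246 deaths = Φ(0.3567 × √246 / 2 − 1.960) = Φ(0.837) = 79.9%.
- With 12 months of follow-up per patient, survival is 0.5^(12/9) = 0.397 on control and 0.397^0.70 = 0.524 on IrPan. The mean probability of death is 1 − (0.397 + 0.524)/2 = 0.540, and 247/0.540 = 458 patients. The plan says 466, which is within 3%.

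The stated 80% therefore reproduces without any covariate.

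**2. Effect of the coding on power.** The protocol gives no performance-status mix and no hazard ratio between levels, so both are assumed. Each simulated trial was analysed twice, with status 0/1 against 2 and with three levels. The hazard ratio of 0.70 holds given performance status, and the hazard ratio of status 2 to 1 is 2.0.

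Design A: 466 patients, 12 months each, mix 36/54/10%, 4,000 trials per row, about 251 deaths.

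| Status 1 vs 0 hazard ratio | Status not in model | 0/1 vs 2 | Three levels | Gain (points) |
|---|---|---|---|---|
| 1.2 | 77.9% | 79.7% | 79.9% | 0.1 |
| 1.5 | 77.0% | 79.7% | 80.4% | 0.8 |
| 2.0 | 75.5% | 79.0% | 81.0% | 2.1 |

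(Gains are taken before rounding: 79.85 − 79.725, 80.425 − 79.65 and 81.00 − 78.95.)

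Design B: 480 patients analysed at 246 deaths, mix 40/50/10%. With 36-month accrual and 1,500 trials per case, power goes from 80.5% to 81.3% (hazard ratio 1.3), 77.1% to 78.9% (1.5) and 77.2% to 79.8% (1.8). A second run of this design gave gains of 0.4, 0.7, 0.8 and 3.2 points at 1.2, 1.3, 1.5 and 1.8.

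The simulation error of a single power is √(0.8 × 0.2/4000) = 0.6 points at 4,000 trials and √(0.8 × 0.2/1500) = 1.0 point at 1,500. The two codings share the same simulated data, so their difference is less noisy than that. Every run points the same way, and the gains lie between 0.1 and 3.2 points.

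**3. Whether the point extends to Ir vs IrCs.** That primary result is an odds ratio "obtained using logistic regression which adjusts for the minimisation factors". From the rates in Section 11.1 the margin as an odds ratio is (0.527/0.473)/(0.633/0.367) = 0.646. With 340 per arm and a true odds ratio of 1:

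- Power without extra covariates = Φ(0.437/√(2/(340 × 0.633 × 0.367)) − 1.960) = Φ(0.786) = 78.4%.
- Adding status 0 vs 1 (assumed 40/60 split) gives 78.3%, 78.1% and 77.4% for covariate odds ratios of 1.3, 1.5 and 2.0.
- Adding K-RAS (wild-type against the rest) gives 78.3%, 78.2% and 77.8%.
- Adding both at 2.0 gives 76.7%.

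On the odds-ratio scale with a fixed margin, extra covariates slightly lower power. A gain appears only on the risk-difference scale (81.8% rising to 83.3% with both at 2.0).

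**4. K-RAS availability.** In the IrPan comparison K-RAS is constant: "Only patients with wild-type *K-RAS* status will be randomised to the Ir vs. IrPan comparison". In the IrCs set, using the shares in Sections 3 and 11.1, wild-type patients number 329 × 0.85 × 0.58 = 162. Unknown status numbers 0.15 × 329 + 421 × 0.15/(0.15 + 0.85 × 0.42) = 49 + 125 = 174, which is 174/750 = 23%.

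**The case against.** The best defence has four parts.

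- **The coding is inferred.** Section 5.2 gives levels for allocation, while Section 12 only says that the model adjusts for the factors. Coding is often left to an analysis plan, and Section 12 says that one exists. This stands in part: if that plan already enters three levels, the point is met. As written, though, the protocol defines the factor by its two levels and ties the primary analysis to it, so the merged form is the natural reading.
- **The data are not wasted.** Section 12 also describes models with further prognostic factors: "will be used to adjust for the minimisation factors and other important prognostic factors" for survival, and "previous anti-EGFR targeted therapy use and any other covariates identified to influence" prognosis for Ir vs IrCs. This stands. Full performance status can enter those models, but they are not the ones that decide the primary result.
- **Nothing falls short of plan.** This stands. The simulated powers just under 80% arise because 0.70 was taken as the effect given performance status, whereas Section 11.1 states it for an unadjusted test.
- **Adjusting for the allocation factors, with wider adjustment as support, is a coherent choice.** This also stands. Three levels respect it, because the merged factor is a collapse of them.

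**Conclusion.** The point holds for the primary Ir vs IrPan survival model, as an improvement and not as an error. Three-level performance status would add roughly 0 to 3 points of power. The gain is near zero if status 0 and 1 have similar survival and reaches 2 to 3 points if the hazard ratio between them is about 1.8 to 2.0. The range rests on assumed mixes (36/54/10% and 40/50/10%) and an assumed hazard ratio of 2.0 for status 2 against 1. It also takes it that the roughly 143 patients from Protocol Version 1 had performance status recorded in full, as Section 7.2 now requires.

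A reader might infer more, because Section 1 says that mutant K-RAS "in lung and colorectal cancers is a poor prognostic factor". The documents do not support these stronger readings:

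- K-RAS is not missing from both primary models in any useful sense, since it does not vary in the IrPan comparison.
- K-RAS is not known for every patient. About 23% of the IrCs set would be unknown, and status for Version 1 patients depends on consent to tissue retrieval (Section 3).
- Adding K-RAS or performance status to the IrCs odds-ratio model does not buy power or the equivalent of extra patients; at a fixed margin it costs a little.
- The stated 80% for overall survival is not undermined.

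**What to change.** Add one sentence to Section 12 (Ir vs IrPan, Primary Endpoint), or to the analysis plan with the change documented: in the primary Cox model for overall survival, WHO performance status at randomisation enters as a three-level factor (0, 1, 2), and the other minimisation factors enter as defined in Section 5.2. Record this before any unblinded efficacy data are seen. Leave the minimisation and the Ir vs IrCs primary model unchanged on this account.

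The cost is one extra model parameter against 246 deaths. No new data, visits or patients are needed.

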5.2.1 Recruitment for Pharmacokinetics (PK) Sub-study

2-4 centres with facilities to perform pharmacokinetic sampling may register to participate in the PK Sub-study. At these centres only, patients who are randomised to receive IrCs may then be invited to consider participating in this sub-study, and provided with the supplementary PK Sub-study Patient Information Sheet and Consent Form document. The original PK sub-study Patient Information Sheet and Consent Form document should be filed in the supplementary PK sub-study Investigator Site File, a copy should be given to the patient and a further copy of the consent form section only sent to the Clinical Trials Research Unit (CTRU). A copy of the PK sub-study Patient Information Sheet and Consent Form document should be filed in the patient

hospital notes if required. It must be made clear that participation is entirely voluntary, and declining the PK Sub-study will in no way affect a patient's participation in the PICCOLO Trial.

Two consecutive treatment cycles of the first four (i.e. cycles 1 & 2, cycles 2 & 3, or cycles 3 & 4) will be nominated as PK Sub-study cycles. The centre will need to complete the PK Sub-study Registration Form and telephone the CTRU on the direct line for 24-hour randomisation in order to randomise the patient to receive, for these two cycles, IrCs and Ir in random order. All other treatment cycles will be with IrCs.

Details of the procedures for PK sampling, sample preparation, storage and transport are given in Appendix 4.

5.3 Baseline and reassessment CT scan

The baseline CT scan **must be within 4 weeks prior to the start of trial treatment**, so a repeat CT should be organised if required, remembering that randomisation cannot take place until *K-RAS* mutation status has been determined. Limited funding is available to contribute towards the cost of repeat baseline CT scans that are required only to meet the timelines set out in this protocol. Funding is available up to a limit of £150 per-patient at the time of writing this protocol. Please contact the CTRU for current funding availability.

Radiological reassessment is made **12 weeks after randomisation** ("12 week scan"), then at 12-weekly intervals, or sooner if clinically indicated, until disease progression ("follow-up scans"). It is recommended that the 12 week scan is pre-booked, at the time of starting treatment, **as near as possible to exactly 12 weeks after the date of randomisation** (with up to a further two weeks allowed in order to take account of practical issues).

If there is clinical evidence of disease progression at a time other than when radiological reassessment is due a CT scan should be carried out to confirm progression. A CT scan should always be carried out to confirm disease progression, unless there is a compelling reason not to.

Please note that copies of the baseline and the 12 week scan are required for external review. The preferred format is CD Rom, but hard-copy films are also acceptable. These should be forwarded to the PICCOLO team, CTRU, University of Leeds, [name] with their reports, as soon as possible after the 12 week scan has been performed. The scans and reports should be anonymised and labelled with the patient's trial number only. CTRU will provide pre-paid Special Delivery envelopes in which to send the CT scans for central review.

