9. CRITERIA OF RESPONSE

Response to treatment will be assessed using the Response Evaluation Criteria in Solid Tumours (RECIST), please refer to Appendix 1. Responses will be confirmed by central review. External confirmation of RECIST response data will be performed on all baseline and 12-week scans.

The baseline and subsequent CT scans (film copies or CD data copies) will be forwarded to the CTRU for external radiological review (see section 5.3).

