Analysis of 12-week assessments will include all patients assessed between 10 and 14 weeks from randomisation. A sensitivity analysis will be conducted to allow for patients assessed outside of this 2 week time frame. Analysis of response will be performed using the centrally reviewed outcome. If the centrally reviewed outcome is missing, the primary analysis will class the patient as being progression-free at 12 weeks (if alive), and a sensitivity analysis will be conducted using the outcome of the local assessment. If this is also missing, the patient will be classed as having progressed at 12 weeks in the sensitivity analysis.

A two-sided 5% significance level will be used for all superiority endpoints, and a one-sided 2.5% significance level will be used for all non-inferiority endpoints.

Safety data (adverse events and serious adverse events as detailed in Section 8) will be presented for all patients by treatment group and comparison, and by relationship to study drug, or underlying colorectal cancer.

Ir vs IrCs comparison

All patients randomised to receive either Ir or IrCs via protocol Version 1.0 or to the Ir vs. IrCs comparison under protocol Version 2.0 (i.e. mutant/unknown *K-RAS* status), regardless of previous anti-EGFR targeted therapy use, will be included in this comparison.

Primary Endpoint

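### A CT showing progression before week 12 has no clear route to central review, and the missing-outcome rule could then count that patient as progression-free in the Ir vs IrCs non-inferiority test.

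*Protocol*

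**What the plan says.** Section 5.3 schedules a CT 12 weeks after randomisation and every 12 weeks after that until progression. It adds an off-schedule scan: "If there is clinical evidence of disease progression at a time other than when radiological reassessment is due a CT scan should be carried out". On central review it tells sites: "Please note that copies of the baseline and the 12 week scan are required for external review". The copies are to be sent "as soon as possible after the 12 week scan has been performed".

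Section 9 makes two statements. The first: "External confirmation of RECIST response data will be performed on all baseline and 12-week scans". The second: "The baseline and subsequent CT scans (film copies or CD data copies) will be forwarded to the CTRU for external radiological review". The second refers back to section 5.3.

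Section 12 sets the data source: "Analysis of response will be performed using the centrally reviewed outcome". Where the central outcome is missing, the primary analysis classes a living patient as progression-free at 12 weeks. The local assessment enters only a sensitivity analysis. Patients who have died without documented progression count as failures in the main analysis.

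The trial is open-label (section 3). The proportion progression-free at 12 weeks is the primary endpoint for Ir vs IrCs and a secondary endpoint for Ir vs IrPan (sections 10.1 and 10.2).

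**The concern.** Take a living patient whose CT at, say, week 7 shows progression. That CT is the evidence for a failure in the primary Ir vs IrCs endpoint. Section 5.3 does not ask for it. Section 9 can be read as asking for it, but limits confirmation to the baseline and 12-week scans. If the 12-week scan is then omitted, or cannot settle the matter, no central outcome exists for a patient who has in fact failed.

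Two readings of section 12 are then open, and the protocol does not choose between them.

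- **Literal reading.** The missing-outcome rule applies and the patient counts as progression-free. If this happens to a similar share of failures in both arms, the observed arm difference shrinks. In a non-inferiority test that makes an inferior regimen easier to pass.
- **Local call counts.** A locally documented early progression is a failure without a central read. These failures then rest on readers who know the allocation, while the 12-week scans are read centrally.

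**Working it through.** **1. The plan's own figure.** Inputs from section 11.1: 63.3% progression-free on Ir, 52.7% as the lowest acceptable rate on IrCs, margin 10.6 points, one-sided 2.5%, 80% power, chi-squared test without continuity correction.

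n per arm = [1.960 × √(2 × 0.58 × 0.42) + 0.842 × √(0.633 × 0.367 + 0.527 × 0.473)]² / 0.106² = (1.368 + 0.584)² / 0.01124, which rounds up to 340 per arm, or 680 in total. The stated 680 is reproduced. Nothing below changes it.

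**2. Expected failures at 375 per arm.**
- Ir: 375 × 0.367 = about 138.
- IrCs at the margin: 375 × 0.473 = about 177.

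**3. Literal reading of section 12.** Let f be the share of true 12-week failures who are alive, progressed on an earlier CT and have no central outcome. The protocol does not give f. It is assumed equal in both arms and shown as a range.

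- Apparent failure rates at the margin: q₁ = 0.367(1 − f) and q₂ = 0.473(1 − f).
- Apparent difference: d = 0.106(1 − f).
- SE = √{[q₁(1 − q₁) + q₂(1 − q₂)] / 375}.
- Type I error = Φ[(0.106 − d)/SE − 1.960].

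For f = 10%: q₁ = 0.3303, q₂ = 0.4257, d = 0.0954, SE = 0.0352. Then (0.0106/0.0352) − 1.960 = −1.66, and Φ(−1.66) is about 4.9%.

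| f (assumed) | Failures counted as progression-free, Ir / IrCs | Apparent difference | One-sided type I error |
|---|---|---|---|
| 0% | 0 / 0 | 10.6 points | 2.5% |
| 10% | 14 / 18 | 9.5 points | 4.9% |
| 20% | 28 / 35 | 8.5 points | 9.0% |
| 30% | 41 / 53 | 7.4 points | 15.8% |

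This is a normal approximation for the unadjusted difference in proportions with all 375 per arm analysed. Section 12 also describes an adjusted odds-ratio analysis. The direction of the effect would be the same there, but its size was not computed.

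**4. If local calls count instead.** Assume site readers falsely call early progression 1 to 5 points more often on one arm.
- Excess on Ir, true rates at the margin: type I error rises to 4.6% (1 point) and 28.1% (5 points).
- Excess on IrCs, true rates equal at 63.3%: power falls from 85% to 78% (1 point) and 35% (5 points).

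The size and direction of such a bias are assumptions. The protocol gives no evidence that it exists.

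**The case against.** **A reader might infer that early-progression scans are never read centrally.** The text does not support that. Section 9 says that subsequent scans are forwarded for external radiological review. The supportable finding is a conflict between 5.3 and 9, and within 9. It still matters, because 5.3 is where sites find the address, format and timing, and it asks for two scans.

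**A reader might infer that early failures in the primary analysis are decided by the unblinded site.** Section 12 as written says otherwise: without a central outcome the living patient is progression-free, and the local call is kept for a sensitivity analysis. Dependence on the site follows only if the protocol intends a locally documented early progression to count without a central read, which it does not say.

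**The 12-week scan may be required in everyone.** Section 7.6 lists it without an exception for patients who have already progressed, section 7.7 makes that exception only for later scans, and section 10.4 speaks of a single mandatory scan. On this reading most early progressors still have a baseline and a 12-week scan for central review. This stands, and it limits how often the missing-outcome rule is triggered. It does not close the gap. Section 7.6 itself collects non-trial anti-cancer treatment given since randomisation, so treatment may have changed before that scan. Appendix 1 judges progression against the smallest sum since treatment started or by new lesions, so a reader with only the baseline and a later scan may miss what the earlier CT showed.

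**A patient count is tempting.** With a 9-month median OS and constant hazard, 1 − 0.5^(2.76/9) = about 19% have died by week 12, leaving about 17.5% alive with progression at the control rate. If 25% to 75% of these were found on an unscheduled CT, that is 33 to 99 of 750 patients. The documents do not support this as an estimate. The 9 months is the planning figure for the Ir vs IrPan comparison, the 25% to 75% is assumed, and the count ignores both the forwarding sentence in section 9 and a 12-week scan done anyway.

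**Conclusion.** The point holds as a collection gap combined with an unresolved classification rule. Sections 5.3 and 9 disagree on which scans go to central review, and section 12 does not say how progression documented before week 12 is classified when no central read exists. Followed literally, the text can turn true failures into successes, which is anti-conservative for the Ir vs IrCs non-inferiority test.

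The size is conditional on f, on f being equal in the two arms, and on the literal reading of section 12. If nearly every early progressor has an informative 12-week scan, f is small and so is the harm. The sensitivity analysis using local assessment would show the problem but would not remove it from the primary result.

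The change is worth making because it is cheap and because the error runs in the direction that favours the claim being tested.

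**What to change.** - **Sections 5.3 and 9:** reconcile them so that the baseline scan and every CT up to and including the 12-week scan are forwarded and centrally read.
- **Sections 9 and 12:** state that progression on a CT before week 12, once centrally confirmed, counts as not progression-free at 12 weeks, so that the missing-outcome rule does not apply to these patients.

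The cost is a few sentences, plus some extra copying, postage and central reads. The scans are already taken under section 5.3 and the central review already exists. The sample size does not change.
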